14.6.4. Vital Signs

Descriptive statistics for vital signs (eg, systolic and diastolic blood pressure, pulse rate, and body weight) and their changes from baseline at each assessment and at the end of treatment will be presented by age and dose group for the single-dose phase and by treatment group for the multiple-dose phase.

14.6.5. Clinical Laboratory Parameters

Descriptive statistics for clinical laboratory values in International System of Units (SI units) and changes from baseline at each assessment time point will be presented by treatment group for each clinical laboratory parameter.

14.6.6. Physical Examination

For each body system, the number and percentage of subjects with transitions from normal or not done at baseline to abnormal post-baseline will be presented by treatment group. The percentages will be calculated relative to the number of subjects having normal or missing assessments at baseline who also had a post-baseline physical examination. A listing of physical examination data for all subjects will also be provided.

14.6.7. Other Safety Measurements

Continuous pulse oximetry, respiratory assessment, neurological assessment will be summarized descriptively by age and dose groups for the single-dose phase and by treatment group for the multiple-dose phase.

14.7. Pharmacokinetic Analyses

14.7.1. Calculation of Pharmacokinetic Variables

PK variables (C_{max} , T_{max} , AUC_{0-t} , AUC_{0-inf} , $t_{1/2}$, CL, and V_d) will be estimated for the single-dose phase from the plasma concentration data using standard non-compartmental methods. Actual sample times, rather than scheduled times, will be used in the computation of PK parameters. Plasma concentrations below the limit of quantification (BLQ) will be set to zero in the computation of mean concentration values; however, BLQ concentrations between 2 non-BLQ concentrations will be set to missing. For the computation of PK variables, the BLQ concentrations prior to the first measurable concentration will be set to zero and other BLQ concentrations will be set to missing.

The definitions and methods of determination for each PK variable are summarized in Table 11.

Table 11: Pharmacokinetic Variables

Variable	Definition
AUC _{0-inf}	Area under the plasma/serum concentration versus time curve from time 0 to infinity, calculated as AUC _{0-t} + C _t /λ _n
AUC _{0-t}	Area under the plasma/serum concentration versus time curve from time 0 to the last measured concentration (C _t), calculated by linear trapezoidal rule
CL	Clearance
C _{max}	Observed maximum plasma/serum concentration; the highest concentration observed during a dosage/application interval
t _½	Terminal half-life, calculated as ln(2)/λ _n
T _{max}	The time at which C _{max} was observed
V _d	Apparent volume of distribution

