- After subjects in Groups C and D are post-operative, and are showing signs of awakening and arousal, their SOC analgesic regimen will be discontinued and they will enter either the single-dose phase of the study.
- ^d Vital signs will include heart rate, respiratory rate, blood pressure, and body temperature.
- ^e Clinical laboratory (chemistry, hematology, and urinalysis) assessments are acceptable for study purposes provided they are taken prior to the first surgical incision and assessed by the Investigator prior to administration of the study drug.
- ^f Respiratory assessment includes oxygen saturation.
- ^g Neurological (sedation) assessments will be completed using the Modified Ramsay Sedation Scale (Appendix A).
- ^h Adverse events (AEs) will be collected from the time of informed consent through 14 days after the last dose of study drug (documented telephone follow-up is required).
- ⁱ Concomitant medications will be collected through 14 days after the last dose of study drug (documented telephone follow-up is required).
- ^j The FLACC will be used for subjects in Groups A and B. The NIPS will be used for subjects in Groups C and D.
- ^k Surgical details must include type of procedure(s), date of procedure(s), surgical start/stop time, and anesthesia/analgesia start and stop time.
- ^l Rescue medication will be administered according to an NCA paradigm, with IV morphine sulfate immediately available.³ The dose of NCA rescue medication will be based on weight and age according to well-established standards.^{4,5}
- ^m Recording of food consumption from the period 1 hour prior to administration of study drug through EOT assessment; record all times that any food was consumed and what food was consumed (diet-as-tolerated [DAT], DAT-soft, full fluids [FF], clear fluids [CF], water, formula, breast milk)
- ⁿ Blood samples for PK analysis should be collected at 0.5 (for subjects with even subject numbers) or 1.0 hour (for subjects with odd subject numbers), and at 2.0, 3.0, 4.0 and 8.0 hours (section 13.1.1). A window of ±10 minutes is allowed.
- Abbreviations: BL=Baseline; EOT=End-of-treatment; ET=Early termination; EKG=Electrocardiogram; NCA=Nurse-controlled anesthesia

³ Czamecki ML, Salamon KS, Jastrowski Mano KE, Ferrise AS, Sharp M, Weisman SJ. A preliminary report of parent/nurse-controlled analgesia (PNCA) in infants and preschoolers. *Clin J Pain*. 2011;27(2):102-107.

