8.1.3. Baseline Dosing Assessments (Day 1, Time 0)

Baseline dosing assessments and procedures should be completed prior to administration of study drug. They include the following:

- Assessing current pain intensity (immediately prior to first administration of study drug): each subject will provide a baseline level of pain intensity using an age-appropriate pain assessment instrument (Face, Legs, Activity, Cry, Consolability [FLACC] scale or Neonatal Infant Pain Scale [NIPS] (Appendix C or Appendix D, respectively) prior to first dose of study drug administration as well as just before administration of each dose of study drug during the multiple-dose.
- Measuring vital signs (section 12.8).
- Continuous pulse oximetry (section 12.10).
- Telemetry (section 12.12).
- Completing a respiratory assessment (section 12.10).
- Completing a neurological assessment (section 12.11 and Appendix A).

Blood sample for baseline PK analysis should be drawn immediately prior to first administration of study drug

- Dosing the subject with study drug (All baseline dosing assessments should be completed prior to administration of study drug)

- When subjects in Groups A and B are showing signs of tolerating oral intake and subjects in Groups C and D are showing signs of awakening and arousal their IV analgesic regimen should be discontinued and the subject will be closely monitored for pain. The pain scores will be recorded at least hourly until time of study drug dosing. Once their pain score is ≥ 3 on the NIPS (day 1 time zero) or is ≥ 4 on the FLACC, study drug (oxymorphone HCl, either IV or oral) can be administered.

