8.3.2. Age Groups C and D

Subjects in age groups C and D will receive a parenteral formulation of oxymorphone HCl (or a matched placebo appropriate for parenteral administration) administered as a bolus dose through their existing IV catheter (already in place for morphine-NCA).

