9.2. Subject Exclusion Criteria

Subjects who meet any of the following criteria will not be eligible to participate in the study:

1. Has the presence or history of a clinically significant disorder involving the cardiovascular, respiratory, renal, gastrointestinal, immunologic, hematologic, endocrine, or nervous system(s) or psychiatric disease that would contraindicate participation, as determined by the Investigator.
2. Has any clinical laboratory test result outside the accepted range that has been confirmed upon re-examination and deemed to be clinically significant.
3. Has a clinically significant illness or condition any time before dosing with study drug that would contraindicate participation, as determined by the Investigator.
4. Has a life expectancy <8 weeks.
5. For age groups A and B: Has a malabsorption, gastroenterologic, or abdominal condition that would interfere with the absorption of study drug.
6. Has evidence of increased intracranial pressure.
7. Has a respiratory condition requiring intubation or resulting in active bronchiolitis, asthma, stridor, or difficulty breathing due to congestion and increased nasal secretions, including O₂ saturation \leq 92%.
8. Has a history of seizures.
9. Subject (and/or mother if subject is nursing) has used medications with actions characteristic of monoamine oxidase inhibitors (MAOIs) within 14 days before the start of the study drug is prohibited. Standard daily pediatric multivitamins may be taken until enrollment into the study but will be restricted during the study.
10. Subject (and/or mother if subject is nursing) has received preoperative opioids for more than 72 consecutive hours.
11. Subject (and/or mother if subject is nursing) has received oxycodone or oxymorphone within 48 hours prior to screening.
12. Subject (and/or mother if subject is nursing) has ingested caffeine- or xanthine-containing products (eg, theophylline) within 48 prior to screening. These products are also prohibited during periods when blood samples are collected.
13. Has a history of relevant drug allergies, food allergies, or both (ie, allergy to oxymorphone or other opioid analgesics) that could interfere with the study.
14. Parent or legal guardian is unable to provide consent for any reason (eg, mental or physical disabilities, language barriers, or is unavailable).
15. Subject (and/or mother if subject is nursing) has participated in a clinical study of an unapproved drug within the previous 30 days.

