14.2.1.1. Single-dose Phase

The safety population for the single-dose phase will include all subjects who receive at least 1 dose of study drug. All safety analyses and demographic/baseline characterization for the single-dose phase will be performed using this population.

The single-dose PK population will include all subjects who receive oxymorphone HCl (immediate-release oral liquid or IV formulation) and provide sufficient data points to facilitate the calculation for non-compartmental PK parameters.

The evaluable population will include all subjects who receive at least 1 dose of the study medication and provide a minimum of 4 hours of post-dose assessments and at least 3 PK assessments to facilitate the dose selection decision. All efficacy analyses for the single-dose phase will be performed on this population.

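### Section 14.7.1 applies one AUC rule to oral and IV-bolus infants; for the bolus groups it misses at least half of the area before the first sample, by an amount that depends on subject number

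*Protocol*

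**What the plan says.** Protocol Section 14.7.1 lists Cmax, Tmax, AUC0-t, AUC0-inf, half-life, CL and Vd, which "will be estimated for the single-dose phase from the plasma concentration data using standard non-compartmental methods". For these variables, "the BLQ concentrations prior to the first measurable concentration will be set to zero". Table 11 runs AUC0-t from time zero to the last measured concentration, "calculated by linear trapezoidal rule". Nothing is split by route.

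The IV infants fall under this rule. Section 14.2.1.1 defines the single-dose PK population as those who receive oxymorphone ("immediate-release oral liquid or IV formulation) and provide sufficient data points to facilitate the calculation for non-compartmental PK parameters"). Section 8.3.2 says the drug in Groups C and D is "administered as a bolus dose through their existing IV catheter".

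The time-zero value comes from Section 8.1.3: "Blood sample for baseline PK analysis should be drawn immediately prior to first administration of study drug". Section 9.2 excludes a child (or nursing mother) who "has received oxycodone or oxymorphone within 48 hours prior to screening", so a pre-dose result below quantification is the expected case. After dosing, Table 3 footnote n has the first sample "collected at 0.5 (for subjects with even subject numbers) or 1.0 hour (for subjects with odd subject numbers"), then samples at 2, 3, 4 and 8 h. Section 8.1.7 adds a 24 h sample where possible.

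**The concern.** Starting the curve at zero is right for an oral dose, where nothing has yet been absorbed. After an IV bolus the concentration is highest at time zero. The rule replaces that peak with zero and joins it by a rising line to the first sample. This lowers AUC and raises CL = dose/AUC.

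The size of the loss depends on when the first sample is taken, and that depends on whether the subject number is even or odd. Cohorts have five infants, so the even/odd mix can move a cohort summary. Observed Cmax and Tmax have the same problem: in a falling curve the highest observed value is the first sample, so they largely report the assigned time. The groups concerned are the youngest infants, in whom the protocol itself expects immature metabolism and reduced renal filtration (Section 6.4.1).

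**Working it through.** **Inputs.** Sampling times, BLQ rule, trapezoid and route are as above. The documents state no AUC, CL or bias figure, so there is none to reproduce. They also give no half-life; I assume 1 to 20 h. Section 14.1.2 lists samples only to 4 h, against 8 h in Table 3 and Section 8.1.5; I use the latter, with and without 24 h.

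**Step 1: a bound that needs no model.** For any falling curve, the true area up to the first sample t1 is at least t1 x C(t1). The rule gives 0.5 x t1 x C(t1). So at most half of the area is captured.

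**Step 2: one compartment, C0 = 1, k = ln 2 / half-life.**
- True first-interval area = (1 - exp(-k t1)) / k
- Area under the rule = 0.5 x t1 x exp(-k t1)
- AUC0-inf = 1/k

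Example, half-life 4 h and t1 = 1 h: k = 0.1733. True area = (1 - 0.8409)/0.1733 = 0.918; rule = 0.420. Missed = 0.498, which is 54.2% of the interval and 0.498/5.771 = 8.6% of AUC0-inf.

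**Step 3: the full rule**, with the tail Ct/lambda (lambda from the last three points) and CL = dose/AUC0-inf.

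| Half-life | First sample | Missed, first interval | Missed, of AUC0-inf | AUC0-inf error, 8 h last | AUC0-inf error, 24 h measurable |
|---|---|---|---|---|---|
| 1 h | 0.5 h | 58.2% | 17.0% | -8.9% | -7.1% |
| 1 h | 1.0 h | 65.3% | 32.7% | -27.6% | -25.8% |
| 2 h | 0.5 h | 54.2% | 8.6% | -4.7% | +6.5% |
| 2 h | 1.0 h | 58.2% | 17.0% | -13.7% | -2.5% |
| 4 h | 0.5 h | 52.1% | 4.3% | -3.2% | +10.2% |
| 4 h | 1.0 h | 54.2% | 8.6% | -7.5% | +5.8% |
| 8 h | 0.5 h | 51.1% | 2.2% | -1.9% | +3.9% |
| 8 h | 1.0 h | 52.1% | 4.3% | -4.1% | +1.7% |
| 20 h | 0.5 h | 50.4% | 0.9% | -0.8% | 0.0% |
| 20 h | 1.0 h | 50.9% | 1.7% | -1.7% | -0.9% |

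The CL error is the reciprocal: at 1 h half-life and 8 h last, 1/0.911 = +9.8% (0.5 h sample) and 1/0.724 = +38.1% (1.0 h sample). Vd, if taken as CL/lambda, carries the same percentage error when lambda is right.

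**Step 4: where the positive errors come from.** At a 4 h half-life, C(8) = 0.25 and C(24) = 0.0156. The linear trapezoid gives 16 x 0.2656/2 = 2.125; the true area is 0.2344/0.1733 = 1.353. The excess, 0.772/5.771 = 13.4% of AUC0-inf, outweighs the early loss. It is not specific to the IV route: for an oral curve with an assumed absorption rate of 1 to 2 per hour and half-life 2 to 4 h, the present rule gives +11% to +17% when 24 h is measurable. With linear-up/log-down that becomes -2% to -6%.

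**Step 5: the fix.** Back-extrapolating C0 but keeping linear trapezoids leaves AUC0-inf up to about +15% (2 h half-life, 24 h measurable). Adding linear-up/log-down brings the one-compartment error to 0%.

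Section 14.1.2 says earlier modelling favoured two compartments but gives no constants. I tried five assumed sets (initial share and half-life / terminal share and half-life), with 8 h last and a 1.0 h first sample:

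| Assumed constants | AUC error, present rule | AUC error, fix | Extrapolated/true C0 (0.5 h; 1.0 h sample) |
|---|---|---|---|
| 0.5, 0.5 h / 0.5, 8 h | -8.7% | -2.9% | 0.85; 0.75 |
| 0.6, 0.25 h / 0.4, 4 h | -13.9% | -5.3% | 0.63; 0.49 |
| 0.8, 0.15 h / 0.2, 8 h | -10.5% | -6.3% | 0.32; 0.22 |
| 0.8, 0.25 h / 0.2, 8 h | -12.8% | -7.0% | 0.52; 0.32 |
| 0.9, 0.1 h / 0.1, 8 h | -13.7% | -10.0% | 0.14; 0.10 |

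**The case against.** **The general wording may already allow C0 back-extrapolation.** Section 14.7.1 does invoke standard methods. But the same section then fixes the zero rule, and Table 11 fixes the trapezoid. An analyst following the specific text would start the bolus curve at zero. This objection does not stand.

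**The effect may be small.** This partly stands. The largest errors sit at the 1 h edge of an assumed range. Section 6.4.1 points towards slower elimination in younger infants, and at 8 h or longer the net AUC0-inf error is within about 4% in the one-compartment model. A reader might infer that half of total exposure is lost; that share belongs only to the first 0.5 or 1.0 h. A reader might also infer that CL is always overstated. The time-zero rule alone does raise it, but the net sign can reverse when the 24 h sample is measurable.

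**Clearance comes from elsewhere.** This stands in part. Sections 14.1.2 and 14.7.2 plan a population model of clearance and volume, which does not use trapezoids or this time-zero rule. Section 13.1.1 names only Cmax, Tmax and AUC0-t as single-dose variables. Section 14.7.1 nevertheless commits to non-compartmental CL and Vd.

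**Dose decisions.** It is tempting to say that the biased values would steer the IDMC. The documents say the IDMC reviews PK, not that it receives non-compartmental parameters, and Group C's starting dose draws on modelling from Groups A and B (Section 8.2). That reading is not supported.

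**The fix is imperfect.** This stands. Under two compartments the extrapolated C0 stays too low and still differs by first sample time. When 24 h is measurable, the two opposing errors of the present rule can by chance land closer to the truth: in the 0.6/0.4 set with a 1.0 h sample, -1.6% against -5.3% after the fix. That cancellation depends on whether a sample taken only where possible exists and is measurable, so it is not a reason to keep the rule.

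**Conclusion.** The point holds as a defect in the protocol text. For IV-bolus subjects the written rule misses at least half of the area before the first sample; this follows for any falling curve. How much that matters for total AUC rests on a half-life the documents do not give. With one compartment and 1 to 20 h assumed, the loss is between about 1% and 33% of AUC0-inf, roughly twice as large for odd-numbered infants, and the net AUC0-inf error is about -28% to +10%. Non-compartmental AUC, CL and Vd in Groups C and D would be biased by an amount tied to subject number, and observed Cmax and Tmax would be largely uninterpretable.

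No reported result is affected. SAP Section 3.1.1 records that nobody was enrolled in Groups C and D, and SAP Sections 7.10 and 8 drop the PK analysis. The correction matters if the protocol text is reused.

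**What to change.** In Section 14.7.1:
- For IV-bolus subjects, obtain the time-zero concentration by log-linear back-extrapolation from the first two post-dose samples instead of setting it to zero.
- Use linear-up/log-down trapezoids for both routes, since the late linear error also affects oral data.
- Report the percentage of AUC that is back-extrapolated.
- In the IV groups, do not interpret observed Cmax or Tmax, and do not compare C0 between odd- and even-numbered infants.
- Name the population PK model as the main source for IV clearance and volume.

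The cost is a few sentences and options that PK software normally offers; no extra blood is drawn. The remaining weakness is two-compartment disposition: for infants first sampled at 1.0 h, AUC stayed about 3% to 7% low in four of the five assumed sets and 10% low in the steepest, which is why the last item is needed. Section 14.1.2 should also be reconciled with Table 3 and Sections 8.1.5 and 8.1.7 on which samples are taken after 4 h.

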14.7.2. Analysis of Pharmacokinetic Results

PK variables will be summarized by age group using N, mean, median, standard deviation (SD), geometric mean, CV, minimum, median, and maximum following dosing in the single-dose phase.

The PK analysis will be conducted using population PK modeling and analysis methods as described in the FDA Guidance for Industry Population Pharmacokinetics. Details of the population PK modeling and analysis will be documented in a separate population PK analysis plan. Results of these analyses will be documented in a separate report.

14.8. Interim Analysis

No interim analysis is planned for this study.

14.9. Statistical Software

Statistical analyses will be performed using Version 9.3 (or higher) of SAS® (SAS Institute, Cary, NC).

15. STUDY DRUG MATERIALS AND MANAGEMENT

15.1. Study Drug Identity

The study drugs are EN3319 oxymorphone HCl prepared as an oral immediate-release solution, matching placebo liquid, oxymorphone HCl IV solution, and sodium chloride 0.9% solution for injection as placebo for oxymorphone HCl IV solution. Oxymorphone oral liquid and IV products are light sensitive and must be protected from light.

15.2. Study Drug Packaging and Labeling

Oxymorphone HCl immediate-release oral liquid 1 mg/mL and matching placebo will be provided in single subject bottles. Each bottle will be labeled minimally with the following information (as appropriate): protocol number, study drug name, strength, dosage form, Class II designation, quantity, lot number, appropriate administration and storage instructions, sponsor's identification and address, appropriate cautionary statements.

Oxymorphone HCl IV solution is supplied as 1 mL units, 10 units/box and each box will be labeled minimally with the following information (as appropriate): protocol number, study drug name, strength, dosage form, Class II designation, quantity, lot number, appropriate administration and storage instructions, sponsor's identification and address, appropriate cautionary statements. Sodium chloride 0.9% solution for injection will be provided with commercial labeling for single use.

15.3. Study Drug Storage

Oxymorphone HCl oral liquid and oxymorphone HCl IV solution must be stored in a locked facility with restricted access in compliance with standards of the Drug Enforcement Administration (DEA) for Schedule II narcotics. Chain of custody of the investigational product will be followed in accordance with the individual site's standard procedures, which will be documented by the site and provided to the sponsor. Store at 25°C (77°F); excursions permitted to 15°C to 30°C (59° to 86°F) [see USP Controlled Room Temperature]. Oxymorphone HCl oral liquid and oxymorphone HCl IV solution are light sensitive and, therefore, must be stored in their original cardboard cartons.

15.4. Study Drug Preparation

Due to light sensitivity, both the oxymorphone HCl oral liquid bottles and the individual units of oxymorphone HCl IV solution must be maintained within the original cardboard carton other than during time of preparation in the pharmacy. The oxymorphone HCl oral liquid or oral liquid placebo dose should be dispensed with an oral syringe (1 mL); the IV oxymorphone solution or saline placebo should be dispensed with an appropriate sterile syringe. Refer to the Clinical Supplies Guidance Document within the Pharmacy Binder for specific instructions for determining and dispensing the appropriate dose. The concentration of both the oxymorphone HCl oral liquid and IV solution is 1 mg/mL. Any oxymorphone HCl oral liquid or IV solution drawn into a syringe should remain protected from light in an envelope or sleeve immediately following preparation until just prior to administration. Any oxymorphone HCl oral liquid drawn into a syringe for administration must be dispensed within 48 hours or returned to pharmacy.

